4.4.7.8 Non-drug Therapies and Procedures

All non-drug therapies and procedures will be coded to SOCs and PTs using the MedDRA dictionary version 21.0. Tables by SOC and PT for the FAS, with SOCs being sorted by decreasing incidence in the overall column, and PTs sorted similarly within SOCs. Subject level listings will be created based on the original CRF data.

4.4.7.9 Post-Treatment Cancer Therapies

Post-treatment cancer therapies are medications or combinations of medications that are captured after the subject has withdrawn from the active treatment period. Each new therapy (single or combination of medications) will be classified by type (hormonal, immunotherapy, chemotherapy, etc.) and counted as a new line of therapy for the purpose of analysis. Analyses based on the number of post-treatment lines of therapy and categories of post-treatment lines of therapy will be performed along with efficacy endpoints.

4.4.7.10 Exposure

Exposure Variables

- Number of CV301 (MVA-BN and FPV) vaccinations received
- Number of atezolizumab treatments received
- Duration of exposure to trial product

Exposure Analyses

Exposure to trial products will be summarized by the number of doses received for each trial product (categorical and continuous summaries) as well as the total duration in days the subject was treated. Duration is calculated as follows:

$$\text{Date of Last Dose of Trial product} - \text{Date of First Dose of Trial product} + 1.$$

Summaries of exposure will be performed by cohort and overall based on the subjects in the FAS. Exposure data will also be listed by subject.

Note, as trial products are given at office visits, treatment compliance is not expected to be an issue. Therefore, no compliance calculations will be performed for the trial.

4.4.8 Safety Variables and Analyses

4.4.8.1 Adverse Events

Variables

- **Baseline Signs and Symptoms (pre-treatment AEs)**
Any AE recorded between ICF signing and first treatment with trial product, regardless of seriousness.
- **TEAEs**
- **SAEs**
- **AESIs**
AESIs include IMAEs and Cardiac events. IMAEs will be collected from the “Potential IMAE” CRF page where the question “Does this event have an immune-mediated etiology or an immune-mediated component?” on the IMAE page is marked as “Yes.” Cardiac AESIs will be identified where “AESI?” is marked as Yes on the AE CRF page. As events coded as “Cardiac disorders” per MedDRA SOC and ECGs with clinically significant abnormalities are considered AESIs, cross checking will be performed to ensure all clinically significant ECG results have a corresponding AE in the database prior to database lock. In addition, Troponin I laboratory testing will also be cross checked versus the AE page in the CRF if results are deemed clinically significant by the investigator.
- **Relationship to trial product (MVA-BN-CV301, FPV-CV301, atezolizumab)**
Relationship is collected as unrelated, unlikely, possibly, probably, or definitely related on the AE CRF page. AEs reported as possibly, probably, or definitely related, along with any missing relationship values, will be summarized as related to the treatment of interest. For overall trial product relationship summaries, if any of the three individual trial products are considered related to the AE, the overall relationship will be defined as related to trial product.
- **Severity of AEs (per CTCAE v5.0 grade)**
TEAEs will be categorized as 1: Mild, 2: Moderate, 3: Severe, 4: Life Threatening, or 5: Death on the AE CRF page. For summaries, severe AE displays will include all AEs \geq Grade 3
- **TEAEs leading to Treatment Discontinuation**
Treatment discontinuation will be identified as an AE with an action taken of “Drug Withdrawn” for any of the three trial products.
- **TEAEs leading to Death**

TEAEs with either an outcome of “Fatal” or a severity of “5: Death” will be considered TEAEs leading to death.

Analyses

Summary tables will be presented by treatment period (MVA Vaccination Period, FPV Vaccination Period, and Overall Treatment Period), cohort, and overall including frequency and incidence of AEs, and ordered by descending incidence of SOCs and PTs for the following categories:

- Any TEAEs
- Non-Serious TEAEs occurring in $\geq 5\%$ of either cohort or overall
- Related TEAEs, including the following subcategories:
 - TEAEs related to MVA-BN-CV301
 - TEAEs related to FPV-CV301
 - TEAEs related to atezolizumab
 - TEAEs related to trial product
- TEAEs \geq Grade 3
- Related TEAEs \geq Grade 3
- SAEs
- Related SAEs
- AESIs, including IMAEs and Cardiac Events
- Related AESIs
- TEAEs leading to discontinuation of treatment

In addition to the above summary categories, listings will also include the following:

- Baseline Signs and Symptoms
- TEAEs leading to death
- Post-treatment period SAEs and AESIs

A summary table of TEAEs will be created for the following categories: TEAEs, SAEs, AESIs, Related TEAEs, Severe TEAEs, Severe and Related TEAEs, Serious and Related TEAEs, TEAEs leading to discontinuation, and TEAEs leading to death. Event counts and subject incidences will be presented within each category and cohort, as well as overall, for the FAS.

The incidence for the above categories will be calculated as the number of subjects developing the specified AE type, divided by the number of subjects in the cohort. The incidence of AEs will also be calculated within each treatment period.

TEAEs will be summarized by SOC and PT and ordered by descending incidence of SOC, as well as descending incidence of PT within SOC. For TEAEs and related TEAEs, summaries will also be provided by

All AEs will be listed by subject, SOC, and PT. Per protocol, no new AEs should be reported during the LTFU phase, with the exception of related SAEs and related AESIs through 100 days post-last treatment. Any other AEs are reported during the LTFU phase will be listed and flagged as non-treatment emergent, but will not be included in the tables.

For summaries by relationship, CRF relationship categories will be dichotomized as related or unrelated per the above definition. Subjects experiencing more than one TEAE within an SOC or PT will be reported for the highest relationship category for the event of interest.

For summaries by severity, the CTCAE v5.0 grade will be used to summarize severe AEs including AEs \geq Grade 3. Again, if a subject has multiple AEs within an SOC or PT the most severe AE will be counted for the event of interest.

A bar chart of TEAEs occurring in $\geq 5\%$ of the either cohort or the overall trial population will be created, with a bar for Cohort 1, Cohort 2, and Overall within PT, and different colors within the bars for related vs. unrelated incidences. Bars will be presented in descending order of PT incidence in the overall cohort.

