### **8.3.2 Reporting of AESIs**

As noted in [Section 8.1.3](#), IMAEs and cardiac events are considered AESIs as well as the AESI requirements from the manufacturer of Tecentriq®. AESIs occurring throughout the reporting period are to be recorded on the AE eCRF by marking the appropriate tick box as well as the (S)AE/AESI eCRF, regardless of seriousness or attribution. AESIs have to be reported immediately after detection. An automatic email notification will be sent to the relevant project members as soon as an AESI has been reported in the EDC. In addition to the above mentioned eCRFs, an IMAE eCRF is also linked to the (S)AE / AESI eCRF in the EDC and must be completed by the investigator when reporting an IMAE AESI.

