A TEAE is an AE with an onset on or after initiation of trial product, or an AE present at initiation of trial product that worsens. This includes all AEs occurring from first dose of trial product through 30 days after of last dose of trial product, if unrelated to trial product or non-serious. All trial product-related SAEs and AESIs through 100 days after the last dose of trial product will be counted as TEAEs.

Related TEAEs

A TEAE is determined to be related to trial product for the purpose of CSR reporting if assessed by the investigator as possible, probable, or definitely related to trial product. If a relationship is missing and the TEAE started after the initiation of an individual trial product, then the TEAE will be analyzed as being related to that individual trial product. Relationship will be collected separately for MVA-BN-CV301, FPV-CV301, and atezolizumab.

Serious Adverse Events

AEs that meet the seriousness criteria as described in Section 8.1.4 of the trial protocol are considered serious adverse events (SAEs). Collection of SAEs begins at the signing of the ICF and continues for 30 days after the last treatment with trial product for unrelated events, and for 100 days after the last dose for treatment-related events.

Severe Adverse Events

AEs are graded for severity using the National Cancer Institute's Common Terminology Criteria for Adverse Events (NCI CTCAE) version 5.0. Levels include 1: Mild, 2: Moderate, 3: Severe, 4: Life Threatening, and 5: Death. For analysis, severe AEs will include AEs \geq Grade 3.

Adverse Events of Special Interest

AEs of special interest (AESIs) include Immune-mediated AEs (IMAEs) and cardiac events but may also include other events based on the opinion of the investigator. Autoimmune diseases and immune-mediated clinical syndromes, occurring after first treatment with trial

product, will be reported as potential IMAEs. In addition, cardiac events are considered AESIs. A Cardiac AESI is defined as:

- Any cardiac sign or symptom (attributed by the investigator to be cardiac related) developed since the first vaccination
- ECG abnormalities determined to be clinically significant developed since the first vaccination

Additionally, for atezolizumab AESIs will be reported based on the manufacturer's requirements (See trial protocol section 8.1.3 for further details).

1 Introduction

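### The SAP's rule for cardiac AESIs has no cardiac condition, so non-cardiac AESIs would be classed as cardiac and unticked cardiac events missed

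*SAP*

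**What the plan says.** SAP 4.4.8.1 gives two derivation rules for AESIs. Immune-mediated events come from their own form: "IMAEs will be collected from the “Potential IMAE” CRF page where the question" about immune-mediated aetiology is answered Yes. For the cardiac group the rule is: "Cardiac AESIs will be identified where “AESI?” is marked as Yes on the AE CRF page". That sentence carries no SOC, preferred-term, ECG or form-type condition, and it does not exclude events that are also on the IMAE page.

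The AE-page box is not reserved for cardiac events. Protocol 8.3.2 states that "IMAEs and cardiac events are considered AESIs as well as the AESI requirements from the manufacturer of Tecentriq", and that "AESIs occurring throughout the reporting period are to be recorded on the AE eCRF by marking the appropriate tick box", whatever their seriousness or causality. The IMAE form is completed on top of that record: "an IMAE eCRF is also linked to the (S)AE / AESI eCRF in the EDC and must be completed by the investigator".

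The AESI entry in the SAP's General Definitions widens the pool further. AESIs "may also include other events based on the opinion of the investigator", and "for atezolizumab AESIs will be reported based on the manufacturer's requirements". The same entry, like Protocol 8.1.3, defines a cardiac AESI more narrowly: a sign or symptom the investigator regards as cardiac, or a clinically significant ECG abnormality, arising since the first vaccination.

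**The concern.** The derivation rule and the definition do not select the same events. The rule takes everything ticked, while the definition takes only cardiac findings. SAP 4.4.8.1 offers no other rule for manufacturer-defined or investigator-opinion AESIs, so the cardiac rule is the only one that picks them up.

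This matters because cardiac safety is a named question for this vaccine class. Protocol sections 2.3.3, 2.5.1.1 and 2.8.1 all discuss cardiac events after poxvirus vaccines and the monitoring built around them. In this trial a routine ECG is scheduled only at Screening, troponin is measured only if clinically indicated (Protocol 8.2.6), and SAP 4.4.8.3 plans no ECG summaries. The classification of adverse events is therefore the main cardiac safety output, and its rule should select what the definition describes.

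**Working it through.** The plan states no figure to reproduce. The check is to apply the rule as written to each kind of event, assuming `AESI?` is a single generic field.

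| Event | AE page `AESI?` | IMAE page | Class under the SAP 4.4.8.1 rules | Cardiac AESI under the documents' own text? |
|---|---|---|---|---|
| Cardiac event, ticked | Yes | – | Cardiac | Yes |
| Confirmed non-cardiac IMAE | Yes | Yes | IMAE and cardiac | No |
| Non-cardiac manufacturer or investigator-opinion AESI | Yes | – | Cardiac only | No |
| Potential non-cardiac IMAE answered No, if the tick is left in place | Yes | No | Cardiac only | No |
| Event in the Cardiac disorders SOC, box not ticked | No | – | Neither | Yes; SAP 4.4.8.1 treats it as an AESI |

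Rows two to four are over-inclusion, and row five is under-capture. Row four is conditional, because neither document says whether the tick is removed once the immune question is answered No.

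The text after the rule does not close either gap. It mentions the Cardiac disorders SOC, but as the reason for checking that each clinically significant ECG has a matching AE. A similar check is described for clinically significant troponin results. Both look for AEs that are absent. Neither removes a non-cardiac event from the cardiac group, and neither confirms that a Cardiac disorders event has its box ticked.

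**Illustrative size.** Inputs:

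- IMAE rate of 12%, from the atezolizumab monotherapy study in first-line cisplatin-ineligible patients described in Protocol 2.1.
- Enrolment of 27 (minimum) to 68 (maximum), from SAP 4.1. Cohort 1 runs from 14 to 33 and Cohort 2 from 13 to 35.

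Expected number mislabelled = rate × n, taking each such subject's event as non-cardiac and ticked:

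- Both cohorts at 12%: 0.12 × 27 = 3.2; 0.12 × 68 = 8.2.
- Cohort 1 alone, the setting the rate comes from: 0.12 × 14 = 1.7; 0.12 × 33 = 4.0.

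For the second-line setting Protocol 2.1 gives only a grade 3–4 immune-mediated rate, 5%. Using it for Cohort 2 as a low figure: 0.05 × 13 = 0.65; 0.05 × 35 = 1.75. Adding Cohort 1 at 12% gives 1.68 + 0.65 = 2.3 at the minimum and 3.96 + 1.75 = 5.7 at the maximum.

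None of these counts includes manufacturer-defined or investigator-opinion AESIs that are not IMAEs, for which the documents give no rate.

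**The case against.** The best defence is that the sentence names a data source and is not a full definition. IMAEs come from the IMAE page and cardiac events from the AE page, with the General Definitions supplying what counts as cardiac. A programmer might well infer the missing filter. The protocol also speaks of the appropriate tick box, which could mean several type-specific boxes, and the eCRF is not available to settle it. This limits the certainty of the finding but does not remove it. The SAP names one field, `AESI?`, with no type attached, and a pre-specified derivation should not depend on inference.

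A reader might go further and infer that the trial will report a false cardiac signal, or bury a true one among immune events. The documents do not support that:

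- No stand-alone cardiac AESI table is named. SAP 4.4.8.1 plans an AESI summary that includes IMAEs and cardiac events, and the table shells are in a separate document.
- Giving an event the wrong subgroup label does not change the total AESI count.
- Tables run by SOC and PT, and every AE is listed, so an immune event coded outside Cardiac disorders still appears under its own SOC and a cardiac event under Cardiac disorders.
- The cardiac AESI summary is descriptive, with no hypothesis test.

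Nor can the figure of 8 in 68 be read as an expectation for this trial. It carries a first-line rate into both cohorts at maximum enrolment.

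**Conclusion.** The rule in SAP 4.4.8.1 is wrong as written and should be corrected. It conflicts with the cardiac AESI definition in Protocol 8.1.3 and the SAP's General Definitions, and it errs in both directions: non-cardiac AESIs are taken in, and unticked Cardiac disorders events are left out.

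The effect is confined to the AESI summary. Over-inclusion distorts the cardiac subcategory. Under-capture could also drop a cardiac event from the AESI summary altogether. In either case the TEAE tables by SOC and PT remain correct.

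The conclusion rests on two assumptions: that `AESI?` is one generic field, and that the rule is programmed literally. The size, about 3 (n = 27) to 8 (n = 68) subjects mislabelled, rests on a third: that the 12% first-line IMAE rate holds in both cohorts and that those events are not cardiac. It shows scale and is not a forecast.

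**What to change.** Replace the cardiac sentence in SAP 4.4.8.1 with an explicit rule. A cardiac AESI is any AE with onset since the first vaccination that meets at least one of these conditions:

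1. It is coded to the MedDRA SOC Cardiac disorders, whether or not `AESI?` is ticked.
2. It is the AE paired with a clinically significant ECG or troponin finding.
3. It is ticked `AESI?` and recorded as cardiac by the investigator, if the CRF captures this. The documents do not show such a field, so check the CRF before relying on this limb.

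The first limb must not require the tick; otherwise the Cardiac disorders events that the section already treats as AESIs would be lost whenever a site left the box blank.

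Keep IMAEs as those answered Yes on the IMAE page. Put all remaining ticked events in a manufacturer/other AESI group, so that they are not counted as cardiac by default. State that an event meeting both the cardiac and IMAE rules appears in both groups and is counted once in the AESI total.

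The cost is a few lines of SAP text and derivation code. The first two limbs use coding, ECG and troponin information that the SAP already relies on.

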## 1.4 Protocol Synopsis

Title	A Phase 2, Multicenter, Single-Arm Trial of CV301 in Combination with PD-1/L1 Blockade in Patients with Locally Advanced or Metastatic Urothelial Bladder Cancer
Clinical phase	Phase 2
Sponsor	Bavarian Nordic A/S 
Number of sites	Approximately 12
Vaccination dose, schedule and administration route	
Prime with MVA-BN-CV301 (nominal titer <math>1.6 \times 10^9</math> Inf.U) given subcutaneously (SC) on Day 1 and Day 22. One dose = four 0.5 mL injections. One injection = nominal titer <math>4 \times 10^8</math> Inf.U in 0.5 mL.
 
Boost with FPV-CV301 (nominal titer of <math>1 \times 10^9</math> Inf.U in 0.5 mL, given SC every 21 days for 4 doses (on days 43, 64, 85, and 106), followed by boosts every 6 weeks until 6 months on trial (i.e., days 148 and 190), then every 12 weeks until completion of 2 years. One dose = one 0.5 mL injection.
 
Atezolizumab fixed dose of 1200 mg intravenous on Day 1 of each 21-day cycle. No dose reduction permitted.

Trial duration	Approximately 104 weeks before starting the long term follow up.
Trial Population	
Patients with Locally Advanced or Metastatic Urothelial Cancer (UC) including bladder, ureter, renal pelvis and urethra.
 
Cohort 1: Ineligible for cisplatin-containing chemotherapy (first-line treatment)
 
Cohort 2: Previously treated with standard first-line cisplatin-based chemotherapy, PD-1/L1 Naïve (second-line treatment)

Number of Subjects:	Approximately up to 68
Primary objectives	Objective Response Rate (ORR; Complete Response [CR] + Partial Response [PR] Rate) as per Response Evaluation Criteria in Solid Tumors version 1.1 (RECIST 1.1)

Secondary objectives	Progression-Free Survival (PFS)  Overall Survival (OS)  Duration of Response  Safety of the treatment combination of CV301 with atezolizumab

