4.3.4 Assignment of AEs to Treatment Period

Each AE will be assigned to a treatment period using date of vaccination (or infusion if this is the final treatment) and date of onset of AE:

- All AEs beginning before the first treatment with trial product will be classified as pre-treatment AEs belonging to the Screening Phase.
- All AEs starting on the day of first MVA-BN-CV301 vaccination until the day prior to the first FPV-CV301, or until early treatment termination, will be assigned to the MVA Vaccination Period.

- All AEs starting after the first FPV-CV301 vaccination through 30 days post-last trial product, or until early termination, will be assigned the FPV Vaccination Period.
- All AEs starting after the first dose of trial product through 30 days post last trial product (CV301 or atezolizumab, whichever is latest) will be included in the Overall Treatment Period.
- Related SAEs and AESIs starting after 30 days but prior to 100 days after the last trial product dose will be assigned to the FU phase of the trial. Other AEs (i.e., not serious or unrelated) occurring during the same time period will be assigned to the FU phase but excluded from tables, if collected, as they are not considered treatment emergent.

If an AE coincides with the date of a vaccination, the AE will be assigned to the treatment period corresponding to the vaccination on this date to be conservative.

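### The SAP has two conflicting rules for a blank causality entry, and the one in section 4.4.8.1 can tabulate an event as FPV-CV301-related before any FPV-CV301 has been given

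*SAP*

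**What the plan says.** Causality is recorded product by product: "Relationship will be collected separately for MVA-BN-CV301, FPV-CV301, and atezolizumab" (SAP General Definitions, Related TEAEs). That definition then deals with blanks. "If a relationship is missing and the TEAE started after the initiation of an individual trial product", it says, "then the TEAE will be analyzed as being related to that individual trial product". The imputation is therefore conditional on timing and confined to the product concerned.

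SAP section 4.4.8.1 (Relationship to trial product) handles the same situation differently. Events in the three upper categories, "along with any missing relationship values, will be summarized as related to the treatment of interest". No onset or first-dose condition appears, and there is no reference back to the General Definitions. The section then defines overall relatedness: an event is related to trial product "if any of the three individual trial products are considered related to the AE". Later in the same section, for the summaries by relationship, "CRF relationship categories will be dichotomized as related or unrelated per the above definition".

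FPV-CV301 starts later than the other two products. MVA-BN-CV301 and atezolizumab begin on Day 1, whereas FPV-CV301 is "given SC every 21 days for 4 doses (on days 43, 64, 85, and 106") (Protocol 1.4). SAP 4.3.4 defines an MVA Vaccination Period made up of "All AEs starting on the day of first MVA-BN-CV301 vaccination until the day prior to the first FPV-CV301". SAP 4.4.8.1 plans a table of events related to FPV-CV301 and presents its tables by treatment period, including that one.

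**The concern.** Both rules are in current SAP text and both derive the same variable, so a programmer cannot follow both. Following 4.4.8.1 as worded, a blank FPV-CV301 entry for an event that began before the first FPV-CV301 dose puts that event in the FPV-related table. The same happens in a subject who stops before FPV-CV301 is ever given. The table for the MVA Vaccination Period could then show FPV-related events although, by definition, no FPV-CV301 has yet been given in that period. Counting a blank as related is a sensible cautious convention for a product the subject has received. It has no such justification for a product not yet received.

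Safety of the combination is a secondary objective and endpoint. The flag feeds the tables of related TEAEs, related TEAEs of Grade 3 or higher, related SAEs and related AESIs.

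**Working it through.** The plan gives no figure here to reproduce. The check sets the two rules side by side, enumerates every pattern of entries, and then converts one reclassified subject into incidence.

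**Inputs**

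- First doses: MVA-BN-CV301 and atezolizumab Day 1; FPV-CV301 planned Day 43 (Protocol 1.4). On schedule, onset on Days 1 to 42 precedes FPV-CV301.
- Each product's entry is related (R: possible, probable, definite), not related (U: unrelated, unlikely) or missing (M). Three products give 3 × 3 × 3 = 27 patterns.
- The General Definitions rule is read as onset on or after the first dose, the reading closest to 4.4.8.1.
- Planned sizes: 14 and 13 at Stage 1, 33 and 35 in full cohorts, 68 overall (SAP 4.1).

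**Relatedness to FPV-CV301, onset Days 1 to 42.** Section 4.4.8.1 says related when FPV is R or M. The General Definitions say related only when FPV is R. They differ whenever FPV is M: 1 × 3 × 3 = 9 of 27 patterns.

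**Relatedness to trial product, onset Days 1 to 42.** With FPV missing, 4.4.8.1 always returns related. The General Definitions return related if MVA-BN-CV301 or atezolizumab is R or M, since both started on Day 1. Of the 9 patterns with FPV missing, 8 therefore agree. The one that differs has MVA-BN-CV301 U, FPV-CV301 M and atezolizumab U, which is 1 of 27.

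**Onset Day 43 or later, FPV-CV301 given.** All three products have started, and the rules differ in 0 of 27 patterns. In a subject who never receives FPV-CV301, the product is never initiated, so the 9 and 1 apply at any onset day.

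These are counts of patterns, not probabilities.

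**Same-day events.** If after initiation is read strictly, the rules also differ for onset on the first-dose day itself. A blank MVA-BN-CV301 entry on Day 1, or a blank FPV-CV301 entry on Day 43, is related under 4.4.8.1 and not under the General Definitions.

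**Size.** The number of reclassified subjects, k, is an assumption, because the documents give no blank rate. Incidence uses the number of subjects in the cohort as denominator (SAP 4.4.8.1), so the shift is 100 × k / N percentage points. At k = 0 it is zero. At k = 1:

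| N | Shift (points) |
|---|---|
| 13 (Stage 1, Cohort 2) | 100/13 = 7.7 |
| 14 (Stage 1, Cohort 1) | 100/14 = 7.1 |
| 33 (Cohort 1) | 100/33 = 3.0 |
| 35 (Cohort 2) | 100/35 = 2.9 |
| 68 (overall) | 100/68 = 1.5 |

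**After the fix.** With the timing condition also written into 4.4.8.1, the rules agree in all 27 patterns at each onset day tested (1, 10, 42, 43 and 60).

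**The case against.** The strongest reply is that the General Definitions already govern. Their entry is headed Related TEAEs and says it serves the study report, and the table category in 4.4.8.1 carries the same name. Section 4.4.8.1 can then be read as a short restatement with the timing condition understood. This is a possible reading, so it is not certain which rule would be programmed. But 4.4.8.1 covers any missing value, and its tables use the definition given above, which is most naturally the one in that section. Two programmers could reasonably produce different tables, and that is enough to require reconciliation.

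A second reply is that blanks may hardly occur. The causality options listed in 4.4.8.1 include no not-applicable choice, and a reader might infer that the FPV-CV301 item will usually be left empty in the first six weeks. The documents do not support that. The list is not a CRF specification, the CRF layout is not given, and an investigator could simply mark unrelated. For SAEs, Protocol 8.3.1 lists the investigator's causality assessment among the minimum contents of the first report. This does not guarantee an entry for each product, but it makes wholly missing causality less likely. This reply stands as a limit on size. It does not remove the conflict.

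Third, no decision uses the flag. The primary endpoint and the two-stage rules do not depend on it, the halting rules in Protocol 4.6.1 rest on review of events by the safety bodies, and all adverse events are listed by subject. This stands in full.

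**Conclusion.** The two rules conflict, and the literal 4.4.8.1 rule gives a wrong result in a defined situation: a blank FPV-CV301 entry with onset before the first FPV-CV301 dose, or in a subject who never receives it. The conclusion rests on reading 4.4.8.1 as worded and on the planned Day 43 start.

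Three stronger conclusions might be inferred and are not supported:

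- That every TEAE in the first six weeks is affected. Only those with a blank FPV-CV301 entry are; their number cannot be computed from the documents and may be zero.
- That the overall related rate is generally inflated. An early event with a blank FPV-CV301 entry does count as related to trial product under 4.4.8.1. The General Definitions give the same answer unless both products already given are recorded as unrelated or unlikely.
- That any attribution to FPV-CV301 of an event that began before it is impossible and should be overwritten. The TEAE definition recognises worsening after initiation, so a recorded assessment may be valid and must stand.

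Each reclassified subject moves incidence by about 3 points in a full cohort, 7 to 8 points if a cohort ends at Stage 1 size, and 1.5 points overall. The effect is confined to descriptive safety tables. It should be corrected before programming.

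**What to change.** In SAP 4.4.8.1, replace the unconditional clause with a rule for missing values only:

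- A missing relationship to a product is imputed as related when TEAE onset, or worsening, is on or after the first dose of that product.
- Otherwise, including when the product was never given, the missing value counts as not related, both in that product's table and in the roll-up to trial product.
- Every recorded investigator assessment is left unchanged, whatever the timing.

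Align the Related TEAEs entry in the General Definitions to the same on-or-after wording. That also settles same-day events consistently with the TEAE definition and with SAP 4.3.4, which assigns an event on a vaccination date to that vaccination's period.

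The cost is one sentence in 4.4.8.1, a matching edit in the General Definitions, and one condition in the derivation program. No change to data collection is needed.
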